6.6 Adverse Event Updates/IND Safety Reports

The sponsor shall notify the Investigator via an IND Safety Report of the following information:

- Any AE associated with the use of drug in this study or in other studies that is both serious and unexpected.
- Any finding from tests in laboratory animals that suggests a significant risk for human subjects including reports of mutagenicity, teratogenicity, or carcinogenicity.

The Investigator shall notify his/her IRB/EC promptly of these new serious and unexpected AE(s) or significant risks to subjects. The Investigator must keep copies of all AE information, including correspondence with the sponsor and the IRB/EC, on file.

6.7 SAE Reconciliation

Reconciliation shall be performed quarterly as an exchange of Line Listings in English. At the end of the Clinical Trial a global reconciliation shall be performed.

7 STATISTICAL CONSIDERATIONS

7.1 Study Design

After patients have signed the informed consent, patients will be enrolled to receive therapy for toxicity and efficacy evaluation. One cycle of therapy is 21 days. No randomization is utilized to assign patients in this study.

The DLT window is 21 days after starting the treatment. The trial starts with safety lead-in:

- Six lead-in patients will be enrolled at dose level 1. If there is one or less DLT, the study will continue following a Bayesian optimal phase 2 (BOP2) design.
- If there are two or more DLTs, the study will enroll another six lead-in patients at dose level -1.
- If there are two or more DLTs at dose level -1, the study of that therapy will be terminated.
- If there is one or less DLT, the study will follow a BOP2 design at the dose level -1.
- The lead-in patients are allowed to be counted as the patients enrolled to stage I per a BOP2 design if they initiate the same dose.

The intent-to-treat (ITT) population includes all patients who have received study agents. Efficacy will be analyzed based on the ITT population, following a BOP2 design ^{86,87} with p_0 (historical response rate) = 15% and p_1 (minimum desired experimental response rate) = 40%. The first stage will consist of 12 patients. Accrual will stop at the end of the first stage if fewer than 3 responses are seen. The second stage will consist of 12 patients. We will declare the experimental agent worthy of further study if 7 or more responses are seen in 24 patients. This design has a Type I error rate of 4.9% and an 86% power. The maximum number of patient enrollment is $6 + 24 = 30$, noting that the lead-in patients will be counted as phase II patients.

Below are the operating characteristics of the design using the BOP2 web application, (Table 11), which is available at <http://www.trialdesign.org>.

Table 11: The Operating Characteristics Of The BOP2 Design For This Study

Scenario	Response Rate	Early Stopping (%)	Claim Promising (%)	Average Sample Size
1	0.15	73.58	4.87	15.2
2	0.30	25.28	55.61	21.0
3	0.40	8.34	86.20	23.0
4	0.50	1.93	97.38	23.8

During the phase II part, after 6 patients are treated, at any time > 30% of patients have DLTs, that dose level will be terminated.

7.2 Statistical Analyses

All patients will be evaluated for toxicity and efficacy from the time of their first treatment. All patients must be assessed for response to treatment to be assigned one of the following categories, even if there are major protocol treatment deviations or if they are ineligible.

- 1) Complete response
- 2) Partial response
- 3) Stable disease
- 4) Progressive disease
- 5) Early death from malignant disease
- 6) Early death from toxicity
- 7) Early death because of other cause
- 8) Unknown (not assessable, insufficient data)

Categorization of response will be based on RECIST 1.1. All of the patients who meet the eligibility criteria (with the possible exception of those who received no study medication) will be included in the main analysis of the response rate. Patients in response categories 4-8 as above should be considered as failing to respond to therapy (disease progression). A patient will be determined as having a response if he/she has CR or PR during the initial 6 months of therapy; a patient will be determined as a non-response if there is no evidence of response by 6 months during this study. Thus, an incorrect treatment schedule or drug administration does not result in exclusion from the analysis of the response rate. In computing PFS and OS, withdrawing patients will be censored at the time of withdrawal.

Wilcoxon's Signed-Rank Test and Fisher's exact test will be used for data analysis of continuous variables and categorical variables, respectively. A mixed model accounting for patient effects will be used to analyze longitudinal data (including biomarker data) over time. For the objective of describing the toxicity profile, descriptive statistics will be provided on the grade and type of toxicity by dose level. The Kaplan-Meier method will be used to estimate PFS and OS.

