5.2 On Study Evaluations

To be obtained weekly during the initial 3 weeks and then as clinically indicated:

- Complete blood count and leukocyte differential and platelet count
- Serum chemistries including sodium, potassium, chloride, carbon dioxide, BUN, creatinine, glucose, calcium, phosphate, magnesium, albumin, alkaline phosphatase, total bilirubin, AST and ALT
- Physical exam including symptoms and signs

ECOG performance status

To be obtained at the beginning of each subsequent cycle:

- Medical history and physical exam
- ECOG performance status
- Assessment of treatment-related and -unrelated toxicities
- Complete blood count with leukocyte differential and platelet count
- Serum chemistries including sodium, potassium, chloride, carbon dioxide, BUN, creatinine, glucose, calcium, phosphate, magnesium, albumin, alkaline phosphatase, total bilirubin, AST, ALT, TSH and free T4
- ECG
- Urinalysis
- Tumor markers, CA125 and/or CA15.3 if elevated at screening
- Women of childbearing potential will have a pregnancy test using blood
- A comprehensive ophthalmological examination, including optical coherence tomography (OCT) of the macula, prior to initiation of therapy, every 2 months for the first 6 months, and every 3 months thereafter will be performed. For onset of visual symptoms, refer patients for ophthalmologic evaluation urgently, with follow-up every 3 weeks until resolution or discontinuation of futibatinib.

To be obtained once every 6-9 weeks for tumor measurement:

- Evaluation of tumor: the same imaging technique or more sophisticated studies will be performed once every 6 weeks of therapy (6 weeks \pm 7 days) for the initial 12 weeks after starting the treatment, and then once every 9 weeks (9 weeks \pm 7 days), or sooner as clinically indicated

Patients will be seen by a physician at the start of treatment and then prior to initiating subsequent cycles (+/- 7 days). In order to more precisely determine time of progression [more precisely](#), the investigator is encouraged to obtain radiological assessments earlier if there is a strong clinical suspicion of progression of disease to either confirm or refute the clinical impression. Possible adverse events will be discussed in detail with each patient and assessed on a continuing basis. ECG, echocardiogram, and other radiological-laboratory tests will be monitored throughout treatment if clinically indicated.

Ophthalmological Examination

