Partial Response (PR): At least a 30% decrease in the sum of diameters of target lesions, taking as reference the baseline sum diameters.

Progressive Disease (PD): At least a 20% increase in the sum of diameters of target lesions, taking as reference the smallest sum on study (this includes the baseline sum if that is the smallest on study). In addition to the relative increase of 20%, the sum must also demonstrate an absolute increase of at least 5mm. (Note: the appearance of one or more new lesions is also considered progression).

Stable Disease (SD): Neither sufficient decrease to qualify for PR nor sufficient increase to qualify for PD, taking as reference the smallest sum diameters while on study.

Response Criteria for Evaluation of Non-target Lesions ([Table 8](#))

Complete Response (CR): Disappearance of all non-target lesions and normalization of tumor marker level. All lymph nodes must be non-pathological in size (<10mm short axis).

Non-CR/Non-PD: Persistence of one or more non-target lesion(s) and/or maintenance of tumor marker level above the normal limits.

Progressive Disease (PD): Unequivocal progression of existing non-target lesions. (Note: the appearance of one or more new lesions is also considered progression).

Evaluation of Best Overall Response ([Table 9](#))

The best overall response is the best response recorded from the start of the study treatment until the end of treatment, taking into account any requirement for confirmation. The patient's best overall response assignment will depend on the findings of both target and non-target disease and will also take into consideration the appearance of new lesions.

Confirmatory Measurement

To be assigned a status of PR or CR, changes in tumor measurements must be confirmed by repeat assessments that should be performed ≥ 4 weeks after the criteria for response are first met. In the case of SD, follow-up measurements must have met the SD criteria at least once after study entry at a minimum interval of 8 weeks.

The duration of overall response is measured from the time measurement criteria are met for CR or PR (whichever is first recorded) until the first date that recurrent or PD is

objectively documented (taking as reference for progressive disease the smallest measurements recorded since the treatment started). The duration of overall CR is measured from the time measurement criteria are first met for CR until the first date that recurrent disease occurs.

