7.3 Stopping Rules

If during the phase II part, after 6 patients are treated, at any time > 30% of patients have DLTs at a dose level, that dose level will be terminated. Another cohort may be started at a lower dose level. In addition, if there are < 3 responses in the first 12 patients, the trial will also be terminated.

Patients may be removed from the study if they meet one of the following stop criteria. However, patients may remain on treatment only in their best medical interest.

- Any uncontrolled side effects affecting quality of life.
- Intercurrent illness that prevents further administration of treatment
- Patients demonstrate at least 20% increase in tumor burden compared with nadir (at any single time point) in 2 consecutive observations at least 4 weeks apart (see below).
- Patients can stop participating at any time. However, if patients decide to stop participating in the study, we encourage them to talk to the researcher and their regular doctor first.
- The researcher may decide to take a patient off this study under several circumstances, such as in the participant's medical best interest, funding is stopped, agent supply is insufficient, patient's condition worsens, and new information becomes available.

- Lead-In Phase:

After the first 6 evaluable patients, complete 21 days of study treatment. IND Office approval must be obtained prior to expanding/changing dose levels.

- Phase II:

Toxicity summary will be submitted after 6 evaluable patients completing 21 days and every six evaluable patients thereafter. During every submission, toxicity data of the previously submitted patients will be updated.

Efficacy summary would be submitted after the first 12 evaluable patients complete 12 weeks of study. Final summary is due after the 24 patients complete 12 weeks of treatment. Responses can be updated till 6 months from the start of treatment.

A copy of the summary report should be placed in the Investigator's Regulatory Binder under "sponsor correspondence".

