Note: Though modified RECIST 1.1 for immune-based therapeutics (iRECIST) criteria ⁸⁷ are not utilized for efficacy assessment in this study, the investigator may decide to continue the treatment beyond tumor progression as defined by RECIST since antitumor response patterns seen with immunotherapeutic agents may extend beyond the typical time course of responses seen with cytotoxic agents. Once the specific criteria of RECIST defined disease progression are met, a repeat efficacy evaluation between 4 and 8 weeks after the initially documented disease progression should be performed in order to confirm disease progression. If the disease progression is confirmed, then the patient may be discontinued. Otherwise, the investigator may decide to continue treatment.

While awaiting confirmation of disease progression, patients may continue to receive study drug, if their clinical status is considered to be stable by the investigator, based on the following criteria (but are not limited to), to ensure that patients are not exposed to unreasonable risk:

- Absence of signs and symptoms indicating clinically significant progression
- Absence of symptomatic or rapid disease progression requiring urgent medical intervention
- No decline in ECOG performance status

The decision to continue study treatment after the first evidence of disease progression is at the discretion of the investigator and requires that the patient agrees to this treatment plan, and that the shared decision to treat beyond progression is documented in source documents. Beyond tumor progression, patients may remain on treatment only in their best medical interest.

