^h) Laboratory tests including CBC with leukocyte differential and platelet count and chemistries (sodium, potassium, chloride, carbon dioxide, BUN, creatinine, glucose, calcium, phosphate, magnesium, albumin, alkaline phosphatase, total bilirubin, AST, and ALT) to be obtained prior to initiation of therapy (C1D1), weekly for the initial 21 days, prior to initiation of each subsequent cycle of therapy, or more frequently as clinically indicated.
ⁱ) Pregnancy test in women of child-bearing potential, urinalysis, ECG, TSH, free T4 and tumor markers (CA125 and/or CA15.3, if elevated at screening) occur within 7 days prior to initiation of therapy (C1D1), and prior to initiation of each subsequent odd cycle of therapy; pregnancy test will continue monthly for at least 3 months after end of therapy; ECHO or MUGA occurs at screening, and then periodically as indicated clinically.
^j) To be performed at screening, once every 6 weeks of therapy (\pm 7 days) for the initial 12 weeks after initiation of therapy, and then once every 9 weeks (\pm 7 days), or sooner as clinically indicated.
^k) To collect peripheral blood samples prior to C1D1, C2D1, and end of therapy or prior to C13D1 if still on therapy.
^l) To request tumor biopsy pre-study if archived tumor tissues (ten 5- μ m thick slides) are not available; biopsy within 1 week prior to C2D1 (at stage II) and at time of relapse in patients with documented SD \geq 6months/CR/PR (optional).
^m) Adverse events to be assessed at all study visits/telemedicine as clinically indicated.
ⁿ) DLT assessment to occur within the initial 21 days of therapy.
^o) Assessments of PRO-CTCAE^T and/or EQ-5D-3L should occur at baseline, then weekly for the initial 6 weeks of therapy (cycle 1), and at the end of each subsequent cycle (subsequent cycles) (optional).

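### For a response first met at the week-21 scan, the confirmation rule, the scan schedule and the 6-month limit do not fit together, so the primary endpoint can be counted two ways

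*Combined protocol and SAP*

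**What the plan says.** Four parts of the combined protocol and SAP decide whether a patient is a responder.

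- **Schedule (5.2, repeated in Attachment A).** Imaging is every 6 weeks "for the initial 12 weeks after starting the treatment, and then once every 9 weeks", each with a 7-day window, "or sooner as clinically indicated". The study calendar lists no separate confirmation scan.
- **Confirmation (5.5).** Changes in tumor measurements "must be confirmed by repeat assessments that should be performed ≥ 4 weeks after the criteria for response are first met". No maximum interval is given, and the repeat need not be a scheduled scan. Table 9 applies the rule: a PR followed by a not-evaluable assessment is at best stable disease.
- **Counting rule (7.2).** "A patient will be determined as having a response if he/she has CR or PR during the initial 6 months of therapy". The same sentence makes a patient a non-responder when nothing shows a response by 6 months. It does not mention confirmation and does not give 6 months in weeks or days.
- **Update limit (7.3).** Efficacy summaries follow 12 weeks on study, and then: "Responses can be updated till 6 months from the start of treatment".

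**The concern.** Week 21 is the only scheduled scan between week 12 and 6 months. It is therefore the only planned occasion on which extending follow-up from the 12-week summary to 6 months can add a new response. A response first met there cannot be confirmed at a scheduled scan until after the limit. The plan does not say whether the 6-month limit governs first observation or confirmation.

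Two analysts could therefore derive different primary endpoints from the same data. On the stricter reading, a week-21 responder's status depends on whether an extra scan was ordered. In an open-label, single-arm trial decided at 7 responses in 24, one reclassified patient can reverse the conclusion.

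**Working it through.** **Schedule arithmetic.** Scheduled scans: 6, 12, 12 + 9 = 21, 21 + 9 = 30, counted from the start of treatment, each ±1 week. Six months = 365.25 / 2 / 7 = 26.1 weeks. Earliest valid repeat = week of first response + 4.

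| First met at | Next scheduled scan | Before week 26.1? | Earliest valid repeat |
|---|---|---|---|
| Week 6 (±1) | 12 (11-13) | Yes | 10 (9-11) |
| Week 12 (±1) | 21 (20-22) | Yes | 16 (15-17) |
| Week 21 (±1) | 30 (29-31) | No | 25 (24-26) |

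Among scheduled scans, only week 21 is affected. An unscheduled repeat at about weeks 25-26 would be in time, with a margin of about one week. If 6 months were counted as 24 weeks (6 × 28 days), a repeat at week 25 would already be late.

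**The two readings.**

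- *Limit on confirmation:* 5.5 withholds CR/PR status until the repeat assessment, and 7.3 stops updates at 6 months.
- *Limit on first observation:* 7.2 requires an absence of any evidence of response for a non-responder. Section 5.5 dates time to initial response and duration of response from when the criteria are first met, and runs best overall response to the end of treatment.

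**The plan's own figures.** Inputs from 7.1: 12 + 12 patients, stop below 3 responses in the first 12, claim at 7 or more of 24, p0 = 15%, p1 = 40%. With b the binomial probability,

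P(claim) = Σ (x = 3 to 12) b(12, x, p) × P[Bin(12, p) ≥ 7 − x].

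This gives 4.87% at p = 0.15 and 86.20% at p = 0.40, as in Table 11.

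**Effect if week-21 responses are not counted.** Let f be the share of responders first seen at week 21. The documents do not give f, so 5% to 20% is an assumption. The countable rate is p × (1 − f), here applied at both stages.

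| f | Rate when p = 0.40 | Power | Rate when p = 0.15 | Type I error |
|---|---|---|---|---|
| 0 | 0.40 | 86.2% | 0.15 | 4.9% |
| 5% | 0.38 | 81.8% | 0.1425 | 3.8% |
| 10% | 0.36 | 76.6% | 0.135 | 3.0% |
| 20% | 0.32 | 63.4% | 0.12 | 1.6% |

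**Separating stage I.** Suppose stage I is judged on the 12-week summary (assumption). Week-21 responses are then missing at stage I whatever the final definition. For f = 10% and p = 0.40, each patient is an early responder with probability 0.36, a late responder with probability 0.04 and a non-responder with probability 0.60. Requiring at least 3 early responses in the first 12, and at least 7 early or late responses in 24, gives 82.0%. Counting early responses only gives 76.6%. The difference, 82.0 − 76.6 = 5.4 points, is the part due to this issue. The other 86.2 − 82.0 = 4.2 points come from reading stage I at 12 weeks.

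**The case against.** A reader might infer that late responders necessarily become non-responders. The documents do not support that.

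- Section 7.2 never requires the confirming scan to fall within 6 months, and a PR recorded at week 21 is evidence of response.
- Even on the strict reading, 5.5 does not tie confirmation to a scheduled visit, and 5.2 allows earlier imaging. A repeat at week 25 meets both rules.
- If the 7-day windows ran from the previous scan and every scan were a week early, scans would fall at weeks 5, 10, 18 and 26, so the last could just confirm the one before it.

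These points stand. The loss is possible, not inevitable.

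A reader might also infer that the true response rate is understated and that the stated 86% power is not delivered. That does not follow either.

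- It needs a share of week-21 responders that the documents do not give. The only timing information for pembrolizumab, in melanoma (section 2.3), is that most responses were seen at the first imaging, at 12 weeks.
- It assumes that all such patients are lost. If half had a week-25 scan, the 10% case gives a rate of 0.38 and power of 82%.
- It assumes that the 40% target refers to response without a time limit. If 40% is the target for the 6-month endpoint as defined, power is 86%.
- The note in 7.3 that "antitumor response patterns seen with immunotherapeutic agents may extend beyond the typical time course of responses seen with cytotoxic agents" justifies treatment beyond progression. It does not say how often first responses appear between weeks 12 and 21.

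What the objection does not remove is the ambiguity. The plan gives no rule for choosing between the readings, and no scan is required that would make them agree.

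**Conclusion.** The point holds as an unresolved counting rule for the primary endpoint. At the scheduled scans it affects only responses first met at week 21. Depending on the reading, such a patient counts, or counts only with a discretionary scan at about weeks 25-26.

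If 5%, 10% or 20% of responders first respond at week 21 and none is counted, power at a 40% true rate is 82%, 77% or 63% instead of 86%. If stage I is read at 12 weeks, about 5 points are due to this issue in the 10% case. These figures rest on the assumed share, on complete loss of those patients, and on 40% meaning response without the time limit. Type I error falls as well, so the risk is missing an active regimen, not a false claim of activity.

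The schedule arithmetic is firm; the size of the effect is not. The rule should be settled before the responses are counted.

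**What to change.** - **Section 7.2:** define a responder as a patient whose CR or PR criteria are first met within 6 months of starting treatment and are confirmed at the next assessment at least 4 weeks later, even if that assessment falls after 6 months.
- **Section 7.3:** let that confirming scan (up to about week 31) update a response first seen by 6 months, and take the final response count after it for the last patient.

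Giving the 6-month limit in weeks would remove the remaining doubt about its length.

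Cost: about two sentences. The final count moves from about week 26 to weeks 30-31 for the last patient, 4-5 weeks later. No scans are added, because week 30 is already scheduled.

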7.3 Stopping Rules

If during the phase II part, after 6 patients are treated, at any time > 30% of patients have DLTs at a dose level, that dose level will be terminated. Another cohort may be started at a lower dose level. In addition, if there are < 3 responses in the first 12 patients, the trial will also be terminated.

Patients may be removed from the study if they meet one of the following stop criteria. However, patients may remain on treatment only in their best medical interest.

- Any uncontrolled side effects affecting quality of life.
- Intercurrent illness that prevents further administration of treatment
- Patients demonstrate at least 20% increase in tumor burden compared with nadir (at any single time point) in 2 consecutive observations at least 4 weeks apart (see below).
- Patients can stop participating at any time. However, if patients decide to stop participating in the study, we encourage them to talk to the researcher and their regular doctor first.
- The researcher may decide to take a patient off this study under several circumstances, such as in the participant's medical best interest, funding is stopped, agent supply is insufficient, patient's condition worsens, and new information becomes available.

- Lead-In Phase:

After the first 6 evaluable patients, complete 21 days of study treatment. IND Office approval must be obtained prior to expanding/changing dose levels.

- Phase II:

Toxicity summary will be submitted after 6 evaluable patients completing 21 days and every six evaluable patients thereafter. During every submission, toxicity data of the previously submitted patients will be updated.

Efficacy summary would be submitted after the first 12 evaluable patients complete 12 weeks of study. Final summary is due after the 24 patients complete 12 weeks of treatment. Responses can be updated till 6 months from the start of treatment.

A copy of the summary report should be placed in the Investigator's Regulatory Binder under "sponsor correspondence".

Note: Though modified RECIST 1.1 for immune-based therapeutics (iRECIST) criteria ⁸⁷ are not utilized for efficacy assessment in this study, the investigator may decide to continue the treatment beyond tumor progression as defined by RECIST since antitumor response patterns seen with immunotherapeutic agents may extend beyond the typical time course of responses seen with cytotoxic agents. Once the specific criteria of RECIST defined disease progression are met, a repeat efficacy evaluation between 4 and 8 weeks after the initially documented disease progression should be performed in order to confirm disease progression. If the disease progression is confirmed, then the patient may be discontinued. Otherwise, the investigator may decide to continue treatment.

While awaiting confirmation of disease progression, patients may continue to receive study drug, if their clinical status is considered to be stable by the investigator, based on the following criteria (but are not limited to), to ensure that patients are not exposed to unreasonable risk:

- Absence of signs and symptoms indicating clinically significant progression
- Absence of symptomatic or rapid disease progression requiring urgent medical intervention
- No decline in ECOG performance status

The decision to continue study treatment after the first evidence of disease progression is at the discretion of the investigator and requires that the patient agrees to this treatment plan, and that the shared decision to treat beyond progression is documented in source documents. Beyond tumor progression, patients may remain on treatment only in their best medical interest.

